
**Cost Effectiveness:** To further inform utility of CHARM2, a cost-effectiveness analysis will be conducted under the direction of [name] using WHO-CHOICE methodology, an internationally accepted standard of economic analysis of health programs. Costs will be collected prospectively and include capital costs (e.g., equipment, space) and recurrent inputs (e.g., FP supplies, administrative costs). Given an expected outcome of improved contraception, costs of increases in non-CHARM2 FP services will be included as partner costs. Costs will be discounted at a rate of 3% per year, per WHO-CHOICE recommendations, varying from 0% to 6% in the sensitivity analysis. Drivers of variation in the total program cost will be assessed using multivariate linear regression. Cost-effectiveness will be calculated by dividing the total program costs by total health outcomes achieved over intervention duration. Outcome measures will include number reached by the CHARM2 and unintended births averted (based on outcome analyses). Based on prior research, we will use an estimate of 3.8 DALYs averted per unintended birth averted. We will also include quantitative measurements of other benefits from unintended pregnancy prevention (e.g., household savings and assets) to capture some of the spill over effects of when unintended pregnancies are prevented. Following WHO benchmarks, the intervention will be categorized as ‘very cost-effective’ if the cost per DALY averted is  $<1x$  the country’s per capita GDP. We will undertake a probabilistic sensitivity analysis, sampling each cost and outcome from an appropriate distribution to determine mean incremental cost-effectiveness, and assess drivers of uncertainty using ANCOVA. Findings will be used to support sustainability and scale up of CHARM2 for use in rural India and elsewhere.

**Sample size considerations:** Treatment effects detectable with 80% power given the 2-armed design with 20 clusters of 48 measurable couples (assuming 80% retention) per arm, or n=960 observed couples. Power calculations took into account multiple levels of clustering, both within-village and within-sub center variance.

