## 11. RECRUITMENT

This study involves randomization at the geographic cluster rather than individual level. While individual randomization is more powerful, cluster randomization allows us to reduce risk for contamination that may occur if both treatment conditions were offered in the same geographic area. Participating couples will be recruited from geographic clusters of approximately equal size mapped for randomization. Clusters are geographically distinct areas with administrative boundaries, natural borders and appropriate distance from other study clusters to reduce risk for contamination. Clusters will be created based on geographic boundaries, population density (approximately 5000 population per cluster), and proximity to ANMs and health providers. Clusters will be selected based on minimum number of eligible couples (at least 60 eligible couples); clusters will then subsequently be randomized to intervention or control conditions using computer-generated random numbers. Households within each cluster will be screened sequentially for eligibility. Research staff are not to be blinded to the treatment condition assignment to clusters. Recruitment of eligible households will be n = 60 per cluster. In a small cluster if the total number of eligible couples is equal to 60, all couples are approached for recruitment. In a larger cluster if the eligible couple number is more than 60, the required number of couples will be selected through systematic random sampling (selecting every nth participant).

Trained NIRRH survey research teams (1 male & 1 female) will approach selected households for screening and recruitment. Three attempts to reach the couple will be made for each selected household. If an eligible household has two or more couples meeting eligibility criteria, a Kish Grid will be used to determine the participants. Couples selected from eligible households will be asked to join the study and will be informed that the study focuses on FP. Data will be collected to assess participation rates and biases by

age, and contraceptive use. Recruitment/enrollment and intervention delivery will occur over 2.5 years on a rolling basis.

**PLEASE NOTE:** No identifiable information will be collected from those screened and found to be ineligible or unwilling to participate, across study phases.

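### The discount-rate sensitivity analysis varies costs only, with no stated rate for DALYs, so it is a weak test of the cost-per-DALY label and may move it the wrong way

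*Combined protocol and SAP*

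**What the plan says.** All of this is in Section 9, under Cost Effectiveness, unless noted.

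- **Discounting:** "Costs will be discounted at a rate of 3% per year, per WHO-CHOICE recommendations, varying from 0% to 6% in the sensitivity analysis". The sentence names costs and nothing else.
- **Health effect:** "Outcome measures will include number reached by the CHARM2 and unintended births averted (based on outcome analyses"), and then "we will use an estimate of 3.8 DALYs averted per unintended birth averted". The value is taken from a cited source. No discount rate, horizon or range is given for it.
- **Ratio:** "Cost-effectiveness will be calculated by dividing the total program costs by total health outcomes achieved over intervention duration".
- **Label:** the programme is classed as very cost-effective "if the cost per DALY averted is" below 1x per capita GDP.
- **Probabilistic analysis:** "We will undertake a probabilistic sensitivity analysis, sampling each cost and outcome from an appropriate distribution to determine mean incremental cost-effectiveness". The paragraph does not say whether 3.8 counts as an outcome here, or whether the discount rate varies.
- **Framework:** the analysis is done "using WHO-CHOICE methodology", with no separate rule for discounting health effects.
- **Timing:** Section 11 says "Recruitment/enrollment and intervention delivery will occur over 2.5 years on a rolling basis". Section 4 gives five years for the whole study.

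**The concern.** A cost per DALY depends on the discount rate through both numerator and denominator. Programme costs arise over a few years, so the rate changes them little. DALYs from an averted birth may accrue over a much longer period, and then the rate matters mainly in the denominator. A sensitivity analysis that varies the rate on costs and leaves 3.8 alone pairs costs at 0% or 6% with DALYs on some other basis. A higher rate then makes the programme look cheaper per DALY.

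At stake is how firmly the very-cost-effective label can be said to withstand the choice of rate. The plan intends the findings to inform sustainability and scale-up. A reader shown a ratio that barely moves between 0% and 6% could conclude that discounting does not matter, when the more sensitive component was not varied.

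**Working it through.** **Nothing to reproduce.** The plan states no programme cost, cost per DALY or GDP figure, and 3.8 is not derived in the document. The check therefore works with ratios to the 3% base case.

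**Inputs from the documents.** Rates 0%, 3% and 6%; 3.8 DALYs per birth; cost period T = 2.5 years (Section 11) or 5 years (Section 4).

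**Assumptions.** Costs are spread evenly over T. DALYs are spread evenly over L years, with L = 10, 20 or 65 to show the range. Let d = ln(1 + r).

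**Step 1: costs only, as written.** Cost factor = (1 − e^(−dT)) / (dT).

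| T | 0% | 3% | 6% | 0% vs 3% | 6% vs 3% |
|---|---|---|---|---|---|
| 2.5 y | 1.000 | 0.964 | 0.931 | +3.7% | −3.5% |
| 5 y | 1.000 | 0.930 | 0.868 | +7.6% | −6.7% |

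With DALYs unchanged, these are also the changes in cost per DALY. If 30 to 50% of cost falls at the start, they shrink to about +1.8 to +5.2% and −1.7 to −4.6%.

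**Step 2: same rate on DALYs.** DALY factor = (1 − e^(−dL)) / d. Relative cost per DALY is the cost factor relative to 3%, divided by the DALY factor relative to 3%.

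| L | DALY factor at 0 / 3 / 6% | Cost per DALY at 0% (T = 2.5 to 5) | Cost per DALY at 6% (T = 2.5 to 5) |
|---|---|---|---|
| 10 y | 10 / 8.66 / 7.58 | ×0.90 to 0.93 | ×1.10 to 1.07 |
| 20 y | 20 / 15.10 / 11.81 | ×0.78 to 0.81 | ×1.23 to 1.19 |
| 65 y | 65 / 28.88 / 16.77 | ×0.46 to 0.48 | ×1.66 to 1.61 |

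Example, L = 20, T = 2.5, 6%: 0.965 / (11.81 / 15.10) = 0.965 / 0.782 = 1.23. Compounding the DALY rate continuously at r instead gives, at 6%, 1.07 to 1.11, 1.20 to 1.25 and 1.63 to 1.69.

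Under these even streams the cost and DALY factors have the same form. Same-rate discounting therefore raises the ratio at 6% exactly when L exceeds T. When L equals T the rate has no effect.

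**Step 3: what this does to the label.**

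- Costs only, 6%: the ratio falls, so the label cannot be lost.
- Costs only, 0%: the label is lost only if the base ratio is at or above 1/1.037 = 0.96x GDP (T = 2.5) or 1/1.076 = 0.93x (T = 5).
- Same rate, 6%, T = 2.5: the label is lost from a base of about 1/1.103 = 0.91x (L = 10), 1/1.234 = 0.81x (L = 20) or 1/1.662 = 0.60x (L = 65).

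**Step 4: the basis of 3.8.** If 3.8 is a 3% figure, the base case is consistent and only the 0% and 6% runs are mismatched. At 6% it would become 3.8 × 11.81/15.10 = 2.97 (L = 20) or 3.8 × 16.77/28.88 = 2.21 (L = 65). If 3.8 is undiscounted, the base case is mismatched too: at 3% it would become 3.8 × 15.10/20 = 2.87 or 3.8 × 28.88/65 = 1.69.

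**The case against.** **Fixed DALYs are inferred from silence.** The plan never says that DALYs are undiscounted or held constant, and it places the analysis within the WHO-CHOICE framework. That stands: a reader might infer a decision to leave health effects undiscounted, and the text does not support this. What the text does show is a rate and range attached to costs, and no rule for the other side of the ratio.

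**The horizon is not in the documents.** The plan does not split 3.8 into mortality and morbidity or say when it accrues. That stands too, and with a 10-year stream the same-rate effect at 6% (7 to 10%) is not much larger than the costs-only shift. The direction needs only that DALYs outlast costs. One person can lose at most about one DALY per year, so 3.8 per birth points beyond a 2.5-year period. It does not prove this, since more than one person may contribute.

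**The check can fail.** A reader might conclude that the analysis would confirm the label whatever the truth. It would not: a base ratio of 0.97x GDP becomes 0.97 × 1.037 = 1.01x at 0%. The check is weak but not empty.

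**A probabilistic analysis is planned.** It samples costs and outcomes and can test the label, including uncertainty in 3.8 if that value is sampled. The plan does not say that it is. Sampling 3.8 would in any case reflect uncertainty about its size and would not re-express it at 0% or 6%.

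**Cost timing is simplified.** Capital and partner costs are included, and the plan does not say whether capital is annuitised. If it were, a higher rate would raise that component, so the costs-only direction rests on the even-spread assumption.

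**Costs-only discounting suits the other outcomes.** For number reached and births averted, which arise over a short period, it is reasonable. The problem is confined to cost per DALY.

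**Conclusion.** The point holds as a flaw in the stated sensitivity rule for cost per DALY. As written, it varies the rate on costs only and uses one DALY multiplier of unstated basis. With costs spread evenly over 2.5 to 5 years it moves the ratio by about 4 to 8% at 0% and 3 to 7% at 6%. If the DALY stream outlasts the cost stream, same-rate discounting moves the ratio the opposite way. At 6% that ranges from about ×1.07 to 1.10 for 10 years to ×1.61 to 1.66 for 65 years, with 3.8 taken as a 3% figure. Those horizons and that basis are assumptions.

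It is tempting to go further and say that CHARM2 would lose its label under consistent discounting. The documents do not support that: they give no cost, GDP or base ratio, so nothing places the programme near the threshold. The issue is limited to the Aim 3 cost-effectiveness analysis and leaves the trial outcome analyses untouched.

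**What to change.** In the Cost Effectiveness paragraph:

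1. State the discount rate and time horizon already built into 3.8.
2. Replace the discounting sentence with: *Costs and DALYs will be discounted at the same rate, 3% in the base case and 0% and 6% in sensitivity analysis. DALYs averted per unintended birth will be re-expressed at each rate from the underlying stream of years lost.* If that stream cannot be recovered from the source, bound it with a short and a long horizon.
3. State that 3.8 is sampled in the probabilistic analysis.
4. Report the cost-effectiveness category at each rate.

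The cost is a few sentences and a little extra analysis, with no new data collection. The downside is that the category may be less favourable at 6%.

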- a) Based on CHARM, we expect the proportion of women using modern contraception in the control group to be 40% at 18 month follow-up. This study will have 83.3% power to detect an absolute difference of 12% or more between treatment groups at follow-up, or 40% vs 52% in the two groups, with total kappa [variance]=0.10, assumed to be split equally between within-village variance and within-cluster variance . These values were found in the CHARM study.
- b) Based on CHARM, we expect that 89.2% of women in the control group will report no recent MSV at 18 month follow-up. We have 91.5% power to detect an absolute difference of 6% or more between treatment groups (89.2% vs. 95.2%) with kappa=0.036,

assumed to be split equally between within-village variance and within-cluster variance. The effect size of 6% difference and the kappa=0.036 were observed in the CHARM study.

c) Based on CHARM, we expect the proportion of women with no unintended pregnancy over 18 month follow-up to be 90% in the control group. This study will have 89.5% power to detect an absolute difference of 5.5% or more between groups (90% vs. 95.5%), with kappa=0. The effect size of 5.5% difference is based on a meta-analysis of cluster RCTs evaluating impact of FP interventions on unintended pregnancy (with comparable measures to this study). The study showed a 50% reduced risk for intervention participants with no unintended pregnancy in the CHARM group, or 5.5%. The kappa=0 is based on the CHARM study, where no significant intra-cluster correlation was found for this outcome.

While we will use longitudinal mixed effects logistic regression methods in our analyses, for power calculations we considered only the 18-month time point in a model similar to those to be used in the analyses. Power for the prescribed longitudinal analyses will be higher. Power calculations for each hypothesis used statistical simulations with 10,000 iterations. The conversion from kappa to the random cluster effect was done using the delta method, and was confirmed through the simulation.

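### Hypothesis (c): a 90% control rate, a 50% risk reduction and a 5.5-point effect cannot all hold; at 90% vs 95%, power is about 80-84%, not 89.5%

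*Combined protocol and SAP*

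**What the plan says.** All the figures are in section 9 of the combined protocol and SAP, under Sample size considerations, mostly in item (c).

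- Control rate: "we expect the proportion of women with no unintended pregnancy over 18 month follow-up to be 90% in the control group".
- Power claim: "This study will have 89.5% power to detect an absolute difference of 5.5% or more between groups (90% vs. 95.5%), with kappa=0".
- Source of the effect: "The effect size of 5.5% difference is based on a meta-analysis of cluster RCTs evaluating impact of FP interventions on unintended pregnancy".
- How the source leads to the effect: "The study showed a 50% reduced risk for intervention participants with no unintended pregnancy in the CHARM group, or 5.5" (the last figure is a percentage).
- Clustering: "The kappa=0 is based on the CHARM study, where no significant intra-cluster correlation was found for this outcome".
- Method: "Power calculations for each hypothesis used statistical simulations with 10,000 iterations".
- General target: "Treatment effects detectable with 80% power given the 2-armed design with 20 clusters of 48 measurable couples (assuming 80% retention) per arm", followed by a total of 960 observed couples.

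No alpha or sidedness is given for the power calculation.

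**The concern.** Item (c) treats a 50% risk reduction and a 5.5-point difference as the same thing. With a control risk of 10% they are not. The effect entered in the power run is therefore larger than the one offered as evidence for it, and the stated power belongs to the larger effect.

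Unintended pregnancy is one of the three outcomes hypothesised in section 6. The lay summary (section 5) says that the original intervention showed no reduction in it, so the meta-analysis is the only support the plan gives for this effect size. If the 50% is what the evidence shows, a reader of item (c) sees a comfortable margin over 80% power that is not there.

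**Working it through.** **Inputs**

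- Control risk: 1 - 0.90 = 0.10 (item c).
- Intervention risk as entered: 1 - 0.955 = 0.045 (item c).
- Couples per arm: 20 x 48 = 960 in total. The Qualitative Data Collection section gives 50/5 = 10 intervention clusters and 20/2 = 10 control clusters, so 960/2 = 480 per arm.
- kappa = 0, so no design effect (item c).
- Two-sided alpha 0.05: an assumption.

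**Step 1: do the three figures agree?**

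- 50% of 0.10 = 0.050, so the cited reduction gives 90% vs 95%.
- 0.055/0.10 = 0.55, so 90% vs 95.5% is a 55% reduction.
- 0.055/0.50 = 0.11, so 5.5 points is a 50% reduction only from an 11% risk (89% vs 94.5%). No section gives 11%.

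**Step 2: reproduce the stated 89.5%**

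Logit form: z = |logit(p1) - logit(p0)| / sqrt[1/(480·p0·q0) + 1/(480·p1·q1)], power = Φ(z - 1.96).

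For 0.10 vs 0.045: z = 0.858/0.268 = 3.205; power = Φ(1.245) = 89.3%.

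Risk-difference form: z = |p1 - p0| / sqrt[(p0·q0 + p1·q1)/480].

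For 0.10 vs 0.045: z = 0.055/0.01664 = 3.304; power = Φ(1.344) = 91.1%.

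Fisher's exact test, enumerated, gives 89.5%. A one-sided test gives 95.1%, 600 per arm gives 95.8% and 960 per arm gives 99.7%. None of these three matches, which supports 480 per arm and a two-sided 0.05.

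**Step 3: the cited 50% reduction, 0.10 vs 0.05**

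Logit: z = 0.747/0.259 = 2.887; power = Φ(0.927) = 82.3%.

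Risk difference: z = 0.05/0.01693 = 2.954; power = Φ(0.994) = 84.0%.

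**Step 4: all methods side by side (480 per arm, kappa=0)**

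| Method | 90% vs 95.5% (plan: 89.5%) | 90% vs 95% | 89% vs 94.5% |
|---|---|---|---|
| Logit Wald, formula | 89.3% | 82.3% | 86.0% |
| Risk difference, unpooled | 91.1% | 84.0% | 87.5% |
| Two proportions, pooled | 90.9% | 83.8% | 87.3% |
| Continuity-corrected | 88.7% | 80.6% | 84.7% |
| Fisher exact, enumerated | 89.5% | 81.4% | not run |
| Logit Wald, simulated (200,000 runs) | 91.5% | 84.3% | 87.9% |
| Same, critical value from t with 18 df | 89.0% | 80.5% | 84.6% |
| Cluster-level t-test, simulated | 88.4% | 80.4% | 84.1% |

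Simulated score and likelihood-ratio tests give slightly more for 90% vs 95% (84.7% and 84.9%), but they overshoot the plan's own contrast (91.7% and 91.9%).

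With 10,000 iterations the Monte Carlo standard error at 89.5% is sqrt(0.895 x 0.105/10,000) = 0.3 points. Methods returning 91% or more are therefore not exactly the plan's. The four closest to 89.5% (Fisher, logit formula, t with 18 df, continuity-corrected) give 80.5-82.3% for 90% vs 95%.

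**Step 5: margin**

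The stated margin over 80% is 89.5 - 80 = 9.5 points. At 90% vs 95% it is about 0 to 4 points. Solving for 80% power from a 90% control rate gives a smallest detectable difference of 4.9 points (logit) or 4.8 points (risk difference), just under the 5.0 that a 50% reduction implies.

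**The case against.** The strongest reply is that the power statement itself is correct. Item (c) claims 89.5% for 90% vs 95.5%, and that reproduces. The fault lies in the sentence that justifies the effect, and at 90% vs 95% the 80% target is still met by every method in the table. All of this stands. It limits the consequence to an effect size without matching support and an overstated margin.

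It can also be said that nobody can tell from the plan which figure is wrong. The justifying sentence is garbled, the 50% or the 90% may be rounded, and the sources are not reproduced. This stands too: 90% vs 95% is one possible correction, not the established one. Two further readings were checked. If 5.5% is the intervention-arm risk (90% vs 94.5%, a 45% reduction), power is 74.2%, but item (c) calls 5.5% an absolute difference and gives 95.5%. If 50% is an odds ratio of 0.5 (90% vs 94.7%), power is 79.0%, but item (c) speaks of reduced risk and again gives 95.5%. Neither reconciles the three figures.

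A reader might infer that the trial is underpowered for this outcome. The documents do not support that. An analytic noncentral-t approximation with 18 df falls slightly below 80% at 90% vs 95%, but it returns only 85.8-87.8% for the plan's own contrast, so it does not represent the plan's method. A reader might also turn this into a challenge to kappa=0. That is a separate design judgement, for which the plan states a basis, and the arithmetic here does not bear on it.

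**Conclusion.** The inconsistency is certain: a 90% control rate, a 50% risk reduction and a 5.5-point difference cannot all be true, and no section reconciles them. The stated 89.5% is correct for 90% vs 95.5% at kappa=0, which is a 55% reduction. It is not the power for the 50% reduction given as its basis.

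If the 50% and the 90% are kept, power is about 80-84%, roughly 5 to 9 points below the stated figure and still at or above the plan's 80%. This rests on 480 per arm, kappa=0 and two-sided 0.05, the last being an assumption. The documents do not settle which of the three figures was intended.

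**What to change.** Rewrite the justification in item (c) so that the control rate, the relative reduction and the absolute difference agree, and restate power from the plan's existing simulation. Three consistent versions are, for example:

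1. 90% vs 95%, a 50% reduction, with about 80-84% power.
2. 90% vs 95.5% with 89.5% power, described as a 55% reduction and with a basis given for that figure.
3. If an 11% control risk was meant, 89% vs 94.5%, a 50% reduction, with about 85-88% power (84.1% by the cluster-level t-test).

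The sponsor has to say which was intended. Stating the alpha and sidedness in the same sentence would remove the one assumption made here.

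The cost is one or two sentences and, for versions 1 and 3, one rerun of the simulation. Sample size, design and analysis do not change.

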## 10. HUMAN SUBJECTS

**NOTE: All subjects will be enrolled at Non-UCSD sites.  
All participants will be of Indian heritage, and enrolled into the study in India.**

**Inclusion of Pregnant Women:** Pregnant women will be included in this study, as the methods meet criteria for their inclusion, including posing no increased risk for the pregnant women or the fetus, beyond that seen for non-pregnant women. Additionally, study findings can support the health of pregnant women, and the study is in no way designed to influence the woman with regard to her choices for the index pregnancy. No additional protections for pregnant women are included, as the existing protections for all wives address risks for pregnant wives (e.g., risk for partner violence).

**Inclusion of Children:** Adolescent wives or husbands included in this study meet the federal definition of children, as they may be under age 21 years. Due to heightened vulnerability in households, very young wives (<18 years) will not be included in this study. We include this population of children as part of our research, but do so without parental consent as they are married and recognized as adults able to provide consent on their own. Study findings specifically support the health and safety of this young population. Existing protections outlined for all wives consider the heightened vulnerabilities young wives face in marriage. Thus, no additional protections are provided beyond that described above. Nonetheless, we have not included wives < 18 years, as the assessments used in this study are not necessarily tailored to the unique needs, sensitivities or cognitive capacities of these younger wives. Further, they are a more vulnerable group that may require greater support than is provided in this study. Our original CHARM study did not identify any wives this young in recruitment.

**Inclusion of Pregnant Children:** Although 18-21 year old pregnant wives may be included, their marital status makes parental consent inappropriate in this context. Research efforts conducted by NIRRH, University of California, San Diego or Population Council will not involve inducements, monetary or otherwise, for pregnancy termination. No members of the research team, including NIRRH research staff members conducting field research, will have any part in decisions related to pregnancy termination. No members of the research team, including NIRRH research staff members conducting field research, will have any part in determining the viability of a neonate.

